5. PROCEDURES

5.1. **[DETERMINATION] Study procedures.** Using lay language, provide a complete description of the study procedures, including the sequence, intervention, or manipulation (if any), drug dosing information (if any), blood volumes and frequency of draws (if any), use of records, time required, and setting/location. If it is available: Upload a study flow sheet or table to **Zipline**.

For studies comparing standards of care: It is important to accurately identify the research procedures. Review the section titled, "When to describe risks for studies evaluating medically recognized standards of care" in the [GUIDANCE Consent](#) and the draft guidance from the federal Office of Human Research Protections, "[Guidance on Disclosing Reasonably Foreseeable Risks in Research Evaluating Standards of Care](#)", October 20, 2014.

Information about pediatric blood volume and frequency of draws that would qualify for expedited review can be found in this [reference table](#) on the Seattle Children's IRB website.

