All study activities will be completed remotely via Zoom or over the phone over the approximately 2 months. Participants will complete a baseline self-report assessment via REDCap (or by telephone, if preferred) that will take approximately 30-45 minutes to complete. At this time, they will also complete a medication collection form with research staff by phone and will be randomly assigned to one of three 4-session telehealth CBT intervention components: (1) relaxation training, (2) behavioral activation, or (3) cognitive therapy. Prior to starting their assigned intervention component, participants will complete a survey consisting of four to eight questions about their fatigue twice per day (morning and evening) for seven days via REDCap (or by telephone, if preferred). They will then complete the 4-session intervention to which they are randomly assigned in approximately 4 weeks. After completing the first intervention session, participants will complete a treatment expectancy measure via REDCap (or by telephone, if preferred). After completing the intervention, participants will complete the post-intervention self-report assessment via REDCap (or by telephone, if preferred) within one month of the last intervention session. During this time, they will also complete a medication collection form with research staff by phone and a survey consisting of four to eight questions about their fatigue twice per day (morning and evening) for seven days via REDCap (or by telephone, if preferred). Qualitative interview data will supplement the quantitative data collected in the post-intervention assessment. Study staff will conduct and audio record semi-structured interviews within one month of completing the last intervention session to query participants about feasibility, acceptability, appropriateness, and perceived efficacy of the intervention component they completed to inform potential component refinement.

5.2. **[DETERMINATION] Recordings.** Does the research involve creating audio or video recordings?

No → Go to [question 5.3](#).

Document Date & Version	APPLICATION IRB Protocol	Researcher Date & Version
01.26.2023 Version 4.3		05/02/2024 Version 1.5 Page 21 of 61

Yes → Verify that you have described what will be recorded in the answer to [question 5.1.](#), and answer question the question below.

5.2.a. Before recording, will consent for being recorded be obtained from subjects and any other individuals who may be recorded?

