- *Restrictions imposed by existing or anticipated agreements (e.g., with third party funders, partners, with repositories, medical centers providing health information under a data use agreement)*

As mentioned above, study data may be analyzed to answer both a priori and post hoc hypotheses related to various aspects of the study behavioral interventions and quality of life issues regarding individuals with MS within the context of rehabilitation medicine.

5.11.f. Consent. Will consent be obtained now from subjects for the secondary use, banking, and/or future sharing?

No

Yes → Be sure to include the information about this consent process in the consent form (if there is one) and in the answers to the consent question in Section 8.

5.11.g. Withdrawal. Will subjects be able to withdraw their data/specimens from secondary use, banking or sharing?

No

Yes → Describe how, and whether there are any limitations on withdrawal.

Example: data can be withdrawn from the repository but cannot be retrieved after they are released.

Study data cannot be withdrawn following data collection or retrieved after they are released.

5.11.h. Agreements for sharing or release. Confirm by checking the box that the sharing or release will comply with UW (and, if applicable, UW Medicine) policies that require a formal agreement with the recipient for release of data or specimens to individuals or entities other than federal databases.

Data Use Agreements or Gatekeeping forms are used for data; Material Transfer Agreements are used for specimens (or specimens plus data). Do not attach any template agreement forms; the IRB neither reviews nor approves them.

Confirmed

5.12. Communication with subjects during the study. Describe the types of communication (if any) the research team will have with already-enrolled subjects during the study. Provide a description instead of the actual materials themselves.

Examples: email, texts, phone, or letter reminders about appointments or about returning study materials such as a questionnaire; requests to confirm contact information.

Staff will email participants notifications to complete online assessments at designated times, call to administer assessments as needed and based on participant preference, check on study progress, and, if the participant is unresponsive to email, call or send text messages.

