Research Manager: Provides direct supervision of the study research staff. In consultation with the study biostatistician, create and manage the study database and ensure tracking of data collection; obtain and maintain UW IRB approval; and assist with the fiscal oversight of the grant including monitoring budget expenditures and making purchase recommendations. Will have extensive experience coordinating similar research trials.

Research Study Assistant: Screen and recruit subjects for study participation; work closely with the research coordinator to maintain the study databases, including monitoring the collection of REDCap survey data and following up with participants who are late in providing assessments; ensure participants are compensated in a timely way for completing assessments; assist investigators with preparation of manuscripts and reports that result from the proposed research. Will have considerable experience working on similar research trials

Biostatistician: Provide advice and guidance with respect to data management and data analysis. Experience applying a variety of statistical methods including survival analysis, clustered data analysis, and logistic regression for clinical trials.

Click or tap here to enter text.

12.4. Study team training and communication. Describe how it will be ensured that each study team member is adequately trained and informed about the research procedures and requirements (including any changes) as well as their research-related duties and functions.

There is no study team

Study team members will also be trained on the attached protocol and manual of procedures. The Site PI and study staff will talk weekly about recruitment and study procedures.

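### Is a one-month limit for the post-intervention measures, with no target day and no stated interview order, too loose?

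*Protocol*

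**What the plan says.** Protocol section 5.1 sets out the course of the study. After baseline and random assignment, participants keep a seven-day fatigue diary before treatment. Then: "They will then complete the 4-session intervention to which they are randomly assigned in approximately 4 weeks". The treatment expectancy measure follows the first session.

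The post-intervention questionnaires come once treatment is finished and "within one month of the last intervention session". On the diary and medication form the section says: "During this time, they will also complete a medication collection form with research staff by phone and a survey". The interview has the same outer limit, as staff hold "semi-structured interviews within one month of completing the last intervention session to query participants about feasibility, acceptability, appropriateness, and perceived efficacy". It is described last and introduced with this sentence: "Qualitative interview data will supplement the quantitative data collected in the post-intervention assessment".

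Scheduling is also mentioned elsewhere. Section 5.12 says: "Staff will email participants notifications to complete online assessments at designated times". Section 12.3 gives the study assistant the task of "following up with participants who are late in providing assessments". Section 12.4 refers to a manual of procedures, which is not among the documents at hand. Section 1.5 puts seven participants in each of three components and lists preliminary efficacy beside feasibility and acceptability. Section 1.8.a names only feasibility and acceptability as what this series examines.

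**The concern.** A pre/post comparison needs a defined post time point. Here a participant assessed on the day of the last session and another assessed about 30 days later both comply, after a treatment of about four weeks. If fatigue drifts once sessions stop, the seven changes in a component mix end-of-treatment status with status at about one month, and the mean change is harder to interpret.

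The second worry is order. The interview asks about perceived efficacy. Held before the questionnaires or during the diary, it could colour the self-ratings, and nothing in section 5.1 rules that out. The form prompt for that section asks researchers to "provide a complete description of the study procedures, including the sequence", so the silence looks like an omission. At stake would be the reading of the preliminary efficacy results.

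**Working it through.** The plan gives no figure on this point to reproduce. The check has three parts: consistency of the text, the possible size of the effect, and what a stricter schedule would achieve.

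**1. Consistency.** Pre-treatment diary 7 days, treatment about 28 days, post-intervention window about 30 days (one month taken as 30 days): 7 + 28 + 30 = 65 days, and 65 × 12 / 365 = 2.1 months. Section 5.1 states approximately two months. The window has a lower bound (treatment finished) and an upper bound (one month). No passage conflicts with it, and no stated figure depends on it.

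**2. Size of the timing effect.** The only inputs from the protocol are n = 7 per component and the one-month limit. The following are assumptions:

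- Lag since the last session is uniform over W days, so SD of lag = W/√12.
- Fatigue drifts by d, in units of the SD of change per 30 days, with d from 0.25 to 1.0.
- The SD of change is multiplied by √(1 + (d × SD of lag / 30)²).

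| Days used | Mean lag | SD of lag | d = 0.25 | d = 1.0 |
|---|---|---|---|---|
| W = 30 | 15 days | 8.66 days | ×1.0026 | ×1.0408 |
| W = 15 | 7.5 days | 4.33 days | ×1.0007 | ×1.0104 |

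The 95% half-width for mean change with n = 7 is t(0.975, 6 df)/√7 = 0.925 SD. With W = 30 it becomes 0.925 × 1.0026 = 0.927 SD at d = 0.25 and 0.925 × 1.0408 = 0.963 SD at d = 1.0.

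**3. What a stricter schedule would achieve.** Suppose questionnaires were due in the first week, the diary followed directly, the interview came only after both, and one month stayed as the outer limit. Assume a share p finishes the questionnaires uniformly over days 0 to 7 and the rest uniformly over days 7 to 30:

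- Mean lag = 3.5p + 18.5(1 − p).
- Variance = p × 49/12 + (1 − p) × 529/12 + 225p(1 − p).

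| p | Mean lag | SD of lag | Multiplier at d = 1.0 | Half-width at d = 1.0 |
|---|---|---|---|---|
| 0.7 | 8.0 days | 7.96 days | 1.035 | 0.957 SD |
| 0.9 | 5.0 days | 5.32 days | 1.016 | 0.939 SD |

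At p = 0.9 and d = 0.25 the SD of change rises by 0.1%. The stricter schedule therefore gives inflation of 0.1% to 3.5%, against 0.3% to 4.1% when the whole month is used. If staff in practice use only about 15 days of the present window, the SD of lag is already 4.33 days, smaller than under the stricter schedule at either p.

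The strict order also strains the one-month limit. Anyone finishing questionnaires after about day 23 could not complete a seven-day diary, and then an interview, by day 30. Under the same model that is 7/23 of late finishers: 0.10 × 7/23 = 3% to 0.30 × 7/23 = 9% of participants.

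**Order of the interview.** Section 5.1 gives a sequence: baseline and assignment, diary, sessions with expectancy after the first, post-intervention assessment with diary, interview. The interview is narrated last and its stated role is to supplement the questionnaire data. Section 5.4 likewise makes it a means of putting the quantitative data in context. Both passages point to the order one would want.

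**The case for a change.** The strongest case for the concern is that assessment timing is a study procedure and is not left to an analysis plan. The upper bound alone does allow end-of-treatment and one-month values to be pooled, and the intended order of the interview is implied without being required. A sentence or two would settle both, with no extra participants or measures. The reading of the text is correct: no target day, diary start day or binding order appears in the document.

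What does not follow is that the plan is wrong or badly fixed. All three components share the window and assignment is random, so the design creates no systematic timing difference between components. The document gives no evidence that an early interview would change ratings. Notifications at set times, follow-up of late participants and a manual of procedures imply a working schedule. Its details cannot be checked here, and their absence from an ethics application form is not an error.

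Nor is a rigid rule free of cost. Making the interview conditional on completed questionnaires and a completed 14-entry diary would, taken literally, lose the interviews of non-completers. They may have the most to say on feasibility and acceptability. Section 10.1 lets participants stop any assessment, and section 4.4 pays for the interview separately.

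**Conclusion.** The concern does not hold. The one-month window is bounded, consistent with the rest of the protocol and common to all components, and the interview is already placed last in the narrative. Carried out as written, a 21-person series mainly about feasibility and acceptability would still give sound results.

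The possible loss is an increase of 0.3% to 4.1% in the SD of change, or a half-width of at most 0.963 SD instead of 0.925 SD at n = 7. That is small beside the imprecision already present with seven people. These figures rest on assumed drift, uniform timing and assumed completion shares; the protocol supplies none of them. What remains is a scheduling preference: a named day would make the post value slightly easier to describe, but its absence is no error.

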See [TIPSHEET Consent Reconsent and Ongoing Subject Communication](#) and [GUIDANCE Consent Reconsent and Ongoing Subject Communication](#) for details.

Study researchers will provide contact information within each point of correspondence in case the participant has questions. In addition, study staff will remind participants during their sessions that their participation is voluntary, that they don't need to participate, and declination won't affect their medical care in any way.

8.3. Electronic presentation of consent information. Will any part of the consent-related information be provided electronically for some, or all of the subjects?

This refers to the use of electronic systems and processes instead of (or in addition to) a paper consent form. For example, an emailed consent form, a passive or an interactive website, graphics, audio, video podcasts. See [GUIDANCE Consent Electronic Consent](#) and [Documentation of Consent](#) for information about electronic consent requirements at UW.

Document Date & Version	APPLICATION IRB Protocol	Researcher Date & Version
01.26.2023		05/02/2024
Version 4.3		Version 1.5

No → Skip to [question 8.4.](#)

Yes → Answer questions **8.3.a.** through **8.3.e.**

8.3.a. Describe the electronic consent methodology and the information that will be provided.

All information materials must be made available to the IRB. Website content should be provided as a Word document. It is considered best practice to give subjects information about multi-page/multi-screen information that will help them assess how long it will take them to complete the process. For example, telling them that it will take about 15 minutes, or that it involves reading six screens or pages.

8.3.b. Describe how the information can be navigated (if relevant).

For example, will the subject be able to proceed forward or backward within the system, or to stop and continue at a later time?

8.3.c. In a standard paper-based consent process, the subjects generally have the opportunity to go through the consent form with study staff and/or to ask study staff about any question they may have after reading the consent form. Describe what will be done, if anything, to facilitate the subject's comprehension and opportunity to ask questions when consent information is presented electronically. Include a description of any provisions to help ensure privacy and confidentiality during this process.

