Protections against risks: Participants will be informed during the consent process and throughout the study they do not have to discuss any topics they do not wish to during treatment or the assessment periods. In addition, participants will be informed in the consent process they are free to stop any session, assessment, or interview at any time. Participants are informed they may refuse to answer any questions that make them feel uncomfortable.

All participants will be clearly informed of their right to withdraw from the study at any point without adversely impacting their routine medical, psychiatric, or psychotherapeutic care.

All participants will be offered the opportunity to discuss any situations or experiences associated with the study procedures that they deem uncomfortable or adverse with the PI, [name].

Telehealth CBT intervention components for MS fatigue: Participants may experience emotional distress when participating in their assigned intervention component, potentially due to increased insight into adaptive and maladaptive behaviors contributing to fatigue management and exerting effort to change their behavior.

Multicomponent CBT consists of Relaxation Training, Behavioral Activation, and Cognitive Therapy, and as a package, CBT has been shown to be an acceptable and effective behavioral intervention for fatigue in adults with MS. Research by the UW investigative team has shown that telephone-delivered (telehealth) CBT is equally as effective as in-person CBT for reducing fatigue in MS and overcomes barriers to accessing specialized care. Last, research also demonstrates that in-person and telehealth CBT for fatigue are feasible and acceptable among patients with MS.

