Provide the name and institutional affiliation of a physician anesthesiologist who is a member of the research team or who will serve as a safety consultant about the interactions between the research procedures and the general or regional anesthesia of the subject-patients. If the procedures will be performed at a UW Medicine facility or affiliate, the anesthesiologist must be a UW faculty member, and the Vice Chair of Clinical Research in the UW Department of Anesthesiology and Pain Medicine must be consulted in advance for feasibility, safety and billing.

Click or tap here to enter text.

*** If the box about radio-isotopes is checked, the study team is responsible for informing in advance all appropriate clinical personnel (e.g., nurses, technicians, anesthesiologists, surgeons) about the administration and use of the radio-isotope, to ensure that any personal safety issues (e.g., pregnancy) can be appropriately addressed. This is a condition of IRB approval.*

10.6. Data and Safety Monitoring. A Data and Safety Monitoring Plan (DSMP) is required for clinical trials (as defined by NIH). If required for this research, or if there is a DSMP for the research regardless of whether it is required, upload the DSMP to **Zipline**. If it is embedded in another document being uploading (for example, a Study Protocol) use the text box below to name the document that has the DSMP. Alternatively, provide a description of the DSMP in the text box below. For guidance on developing a DSMP, see the [IHS webpage on Data and Safety Monitoring Plans](#).

PI [name] will follow the full DSMP description found on page 160 of the research grant

10.7. Un-blinding. If this is a double-blinded or single-blinded study in which the participant and/or relevant study team members do not know the group to which the participant is assigned, describe the circumstances under which un-blinding would be necessary, and to whom the un-blinded information would be provided.

N/A

10.8. Withdrawal of participants. If applicable, describe the anticipated circumstances under which participants will be withdrawn from the research without their consent. Also, describe any procedures for orderly withdrawal of a participant, regardless of the reason, including whether it will involve partial withdrawal from procedures and any intervention but continued data collection or long-term follow-up.

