Participants could potentially be withdrawn without consent. In the past this has been very rare. Typically happening in instances where the participant becomes unable to contact despite frequent calls from study staff. PIs also reserve the right to withdraw subjects if they feel it is in their best interest (in cases where procedures could be contributing to suicidal ideation). However, suicidal ideation is not expected to be a risk in this study.

10.9. [DETERMINATION] Anticipated direct benefits to participants. If there are any direct research-related benefits that some or all individual participants are likely to experience from taking part in the research, describe them below:

Do not include benefits to society or others, and do not include subject payment (if any). Examples: medical benefits such as laboratory tests (if subjects receive the results); psychological resources made available to participants; training or education that is provided.

Members of this team have run previous studies with therapeutic skills taught in the planned study support. Based on this research, we anticipate that participants will experience reductions in their daily fatigue and other benefits associated with the treatment.

In this past research, many study participants have expressed satisfaction from receiving treatment in a caring and nonjudgmental environment. Thus, participants in treatment will take away from the study new skills and knowledge regarding fatigue and how to manage it and should experience some degree of relief and increases in their quality of life.

10.10. [DETERMINATION] Return of individual research results.

In this section, provide your plans for the return of individual results. An “individual research result” is any information collected, generated or discovered in the course of a research study that is linked to the identity of a research participant. These may be results from screening procedures, results that are actively sought for purposes of the study, results that are discovered unintentionally, or after analysis of the collected data and/or results has been completed.

See the [GUIDANCE Return of Individual Results](#) for information about results that should and should not be returned, validity of results, the Clinical Laboratory Improvement Amendment (CLIA), consent requirements and communicating results.

10.10.a. Is it anticipated that the research will produce any individual research results that are clinically actionable?

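### Do participants who stop sessions early fall outside the post-intervention assessment and interview?

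*Protocol*

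**What the plan says.** Protocol section 5.1 sets out one path for everyone. On treatment: "They will then complete the 4-session intervention to which they are randomly assigned in approximately 4 weeks". On what comes next: "After completing the intervention, participants will complete the post-intervention self-report assessment via REDCap", in the month after the last session, with the medication form and the seven-day diary in the same period. The interview has the same limit: staff hold "interviews within one month of completing the last intervention session to query participants about feasibility, acceptability, appropriateness, and perceived efficacy", and its subject is the perceived "efficacy of the intervention component they completed to inform potential component refinement".

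Stopping early is foreseen. Section 10.1 tells participants that "they are free to stop any session, assessment, or interview at any time", and section 8.2.f adds that "study staff will remind participants during their sessions that their participation is voluntary".

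The form's prompt at section 10.8 asks about orderly withdrawal, including "whether it will involve partial withdrawal from procedures and any intervention but continued data collection or long-term follow-up". The study's answer covers withdrawal without consent. Of that it says: "Typically happening in instances where the participant becomes unable to contact despite frequent calls from study staff". It then adds withdrawal by the investigators in the participant's interest. It does not mention a person who gives up the sessions but stays in the study.

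**The concern.** Read literally, the schedule starts from finishing all four sessions, and the interview concerns a component that was finished. Someone who leaves after session 2 has then no stated assessment time, and section 10.8, where the form asks about continued data collection, is silent.

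The stake is the study's main aim. Section 1.8.a gives feasibility and acceptability of each component as what the case series examines, and sections 5.1 and 5.4 use the interview to refine the components. People who stop because a component did not suit them know something that completers do not. If they were never asked, the component would probably look more acceptable than it is, and no analysis can recover an interview that was not held.

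**Working it through.** The protocol states no rate of stopping and no acceptability proportion, so there is no planned figure to reproduce beyond 3 × 7 = 21, which agrees with section 1.5. The check is first textual, then a matter of scale.

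**1. Is there a completers-only rule?**

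| Place in the Protocol | What it fixes | Limited to completers? |
|---|---|---|
| 5.1 | Order of events; post-treatment data after the intervention, within a month of the last session | Order only; excludes no one |
| 1.5 | Measures, diary and interview at post-intervention; medication form at post-treatment | No |
| 5.4 | Post-intervention assessment and interview | No |
| 4.4 | Payment for each assessment done | No |
| 5.4, contact information | Other people to call if a participant cannot be reached | No |
| 5.12 | Email notices at set times, then calls or texts | No |
| 12.3 | Staff pursue late assessments | No |
| 10.1 | Stopping a session and withdrawing from the study are described separately | No; stopping a session is not withdrawal |

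Only the wording of 5.1 leans towards completers. Nothing ends assessment for someone who stops sessions.

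**2. Does an early stopper have a window?** If the last session means the last one attended, yes. With 4 sessions in about 4 weeks, evenly spaced (an assumption), someone who stops after session 2 has a window that opens about two weeks before a completer's. Taking a month as about four weeks, the windows run from roughly week 2 to week 6 and from week 4 to week 8, so they overlap. If the last session means session 4, no window is stated. The text supports either reading, so this is an ambiguity and not a demonstrably absent time.

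**3. Scale.** Let p be the chance that a participant stops early, independently of others. The protocol gives no value. The nearest figure is retention above 90% in past studies (section 4.1), which would mean fewer than 0.10 × 21 = 2.1 people lost, but study retention is not session completion. The range for p is therefore assumed.

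- Expected among 21 = 21p
- Expected per component = 7p
- P(at least one of n) = 1 − (1 − p)^n
- P(at least two of 7) = 1 − (1 − p)^7 − 7p(1 − p)^6

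| p | Expected of 21 | Expected of 7 | P(≥1 of 21) | P(≥1 of 7) | P(≥2 of 7) |
|---|---|---|---|---|---|
| 0.05 | 1.05 | 0.35 | 0.659 | 0.302 | 0.044 |
| 0.10 | 2.10 | 0.70 | 0.891 | 0.522 | 0.150 |
| 0.15 | 3.15 | 1.05 | 0.967 | 0.679 | 0.283 |
| 0.20 | 4.20 | 1.40 | 0.991 | 0.790 | 0.423 |

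At least one early stopper is therefore likely somewhere in the study.

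**4. What one missed stopper could do.** With six satisfied completers and one dissatisfied stopper who is not asked, a component scores 6/6 = 100% instead of 6/7 = 86%, a gap of 14 points. That needs three things together: the stopper is dissatisfied, nobody asks, and acceptability is summarised as a proportion. The protocol establishes none of them. If the stopper is asked, or holds the same view as the completers, the gap is zero.

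**The case for a change.** The best argument for a change is that this is a rule about collecting data, not about analysing it. It therefore belongs in the protocol, and the prompt at section 10.8 asks for it almost in so many words. Three expressions in section 5.1 point to completion. The notices and the pursuit of late assessments presuppose a due date, which an early stopper may not have. Closing the gap would take a few words and, at an assumed 5% to 10%, cost about $40 × 1.05 = $42 to $40 × 2.10 = $84 in participant payments (two payments of $20 each, section 4.4).

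Much of this stands. Section 5.1 is ambiguous, section 10.8 leaves part of its prompt unanswered, and the quantities above are right for the rates assumed. What does not follow is that the plan is wrong. No stated rule gives a wrong result and no two statements contradict each other. Section 5.1 answers a request for a plain-language account of procedures in sequence, and it gives the usual course. The operating detail may sit elsewhere: section 12.4 refers to a manual of procedures, section 5.4 to a list of interview questions, section 5.15 to uploaded forms, and section 8.2.b to an information statement. None of these is available here, so their silence cannot be assumed.

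**Conclusion.** No change to the plan follows. The concern identifies an unwritten detail, not a completers-only rule. Staff who keep in touch with participants, hold alternative contacts and pay for each assessment would probably invite someone who stopped early to the questionnaires and interview, especially when the purpose is to learn how to refine the component.

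The size is unknown. Under assumed stopping rates of 5% to 10%, one or two people among 21 would be affected, each one seventh of a component, and the bias runs from zero to about 14 points for one such person in a component. The upper figure rests on a dissatisfied stopper who is never approached and on an acceptability proportion that the protocol does not define.

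The conclusion assumes that stopping sessions is not treated in practice as leaving the study. The protocol nowhere says that it is, and section 10.1 describes the two separately. Clearer wording would be a courtesy to the reader and is optional.
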